5.1. Subject Recruitment and Screening

Patients will be recruited during preoperative visits through normal referral practice.

If the patient fulfills the study criteria, the surgeon informs the patient concerning the study and gives the information letter. The surgeon will answer remaining questions at the next visit. If the procedure is clear and the patient agrees to participate, the informed consent is signed and the preoperative questionnaires are obtained. All patients recruited for this study will have the capacity to give their informed consent on the ethics committee approved, study specific Informed Patient Consent Form. If the patient does not want to participate or does not fulfill the inclusion criteria, he/she will obtain the normal clinical follow-up.

5.2. Patient Informed Consent and Guidelines

The subject will be informed by the Investigator (or his designated representative) of the purpose of the study, study duration, and follow-up schedule. All foreseeable risks and potential benefits, which might occur during and after total knee arthroplasty, will be discussed with the subject.

The subject will be informed that his/her medical records are subject to review by representatives of the sponsor as necessary. The confidentiality of the subject will be maintained at all times. The subject will be told that he/she is free to refuse study participation or to withdraw from the study at any time without compromising future medical care.

All subjects for this study will be provided with a consent form describing this study giving sufficient information for subjects to make an informed decision about their participation in the study.

The informed consent must contain all elements required by local and institutional policies. See Appendix 1 for a copy of the Patient Information Sheet and Informed Consent Form. The document must be translated into the local language(s) applicable in each study site, be understandable to the subject and must specify who informed the subject. When required by local regulations, the person informing the subject must be a physician. This consent form will be submitted with the protocol for review and approval by the IEC/IRB for the study.

All subjects must provide written consent of their willingness to participate in the study after having had adequate time to consider their decision. The formal consent of a subject, using the EC-approved consent form, must be obtained before that subject is submitted to any protocol related procedures that are not part of the subject's normal care. Written documentation of consent must be provided on the consent's signature page in addition to a note in the patient medical records indicating the date that consent was obtained. The investigator obtaining the consent must also sign this consent form. The subject or their legal representative should receive a signed copy of the consent.

5.3. Randomization, Blinding and Treatment Allocation

The patients will be randomized to receive N2Vac polyethylene inlay or the X3 polyethylene inlay (see section 3.3). The randomization will occur via a random number generator (manual or computer). The doctor or other health care professional does not choose the participants for each group. For patients satisfying inclusion criteria, randomisation will occur by retrieving the next randomly generated group assignment. The patient, physiotherapist (for the clinical evaluation) and data analyzers (RSA data, clinical data, radiographic data and statistics) will be blinded. The PI and other participating surgeons have no influence on the collection of the (clinical) data and the data analysis.

5.4. The Operative Procedure

The prosthesis is placed according to the instruction manual (see appendix) by an experienced knee surgeon using a standard approach and instrumentation.

5.5. The Postoperative Treatment

The patient will rehabilitate at home with help of a physiotherapist. At the regular visits at the outpatients the questionnaires will be obtained by a physiotherapist (blinded to which patient received which type of inlay). The physiotherapist was not present at the operation. The patients will complete the patient questionnaires by himself/herself. In case of a complication or adverse event, the surgeon will be called.

5.6. Supplies/Device Accountability

The study devices must be stored and handled in accordance with the manufacturer's guidelines. The Investigator will also keep accurate records of the devices assigned to each subject.

The investigator will be asked to attach the labels (with the lot device number), where possible, of the implanted devices to the corresponding patient CRF page in order to keep a tracking of the devices.

6. Methods and Evaluations

Subjects will be evaluated preoperatively, prior to discharge and at follow-up intervals of 6 weeks, 3 months, 6 months, 1, 2 and 5 years. Each subject will be followed for five years post-implantation. At the 1-year follow-up a double examination will be made in order to assess the clinical RSA precision. All subject evaluations will be documented by completion of appropriate Case Report Forms (see Appendix 2).

Table 1 – Evaluation schedule (functional and patient assessment)

	Pre-op	Op	< 1wk (prior to discharge)	6wk	3m	6m	1yr	2yr	5 yr
Range (weeks)				±4d	±1wk	±2wks	±4wks	±4wks	±6ks
Demographic Information	✓								
Historical Record	✓								
Clinical Evaluation			✓	✓	✓	✓	✓	✓	✓
Operative Record		✓							
Knee Society Score	✓			✓	✓	✓	✓	✓	✓
SF-36	✓			✓	✓	✓	✓	✓	✓
EQ 5-D	✓			✓	✓	✓	✓	✓	✓
Lower-Extremities Activity	✓			✓	✓	✓	✓	✓	✓
RSA analysis			✓	✓	✓	✓	✓ (double)	✓	✓
Radiographic imaging	✓ AP/		✓ Lat	✓	✓ Lat	✓	✓ Lat	✓ Lat	✓ Lat

	Lat							
Adverse Events (including revision)		Anytime						

Basic demographic and medical history information is to be collected at the most two months prior to surgery. This information includes age and gender. Height, weight, primary diagnosis, concurrent medical condition and prior treatment to the affected joint are also documented at this time.

Prior to surgery (- 2 months)

Demographic information:	Date of birth Height/ weight Gender	
Patient's initial diagnosis		
Operative side		
Historical record	Cigarette Smoker Medical History: Concurrent Medical condition and current treatment according to medication category (ATC Class)	
Am. Knee Society Score AKSS*	Pain intensity Active and passive range of motion (Neutral-zero-method) Stability Anatomic alignment Walking/standing ability Stair climbing ability Use of walking aids	
Patient questionnaires	SF-36 EQ-5D LEAS (Lower Extremities Activity Scale)	
Radiographic assessment	Anterior/posterior Lateral	

Surgical Procedure

Anesthesia	Type ASA	
Systemic prophylactic therapy	Antibiotic	

	Anticoagulant	
Bone cement		
Surgical approach		
Soft tissue released		
Navigation		
Deviation from site-specific surgical procedure		
Bone removed	Femur Tibia Slope	
Tantalum balls (ø 1.0 mm)	Position in the tibia bone	
Time	Skin to skin Tourniquet	
Implant details	Sizes of components Product labels	
Intra-operative complications		

Assessment at on week postoperative

Clinical evaluation	Concomitant therapy	Pain medication
	Systemic prophylactic therapy	Antibiotic Anticoagulant
	Rehabilitation/mobilization	Site specific procedure Discharged
Radiographic assessment	Anterior/posterior Lateral Radiostereometric analysis	
Early post-op complications		

Follow-up assessment at 6 weeks, 3 months, 6 months, 1 year, 2 years and 5 years

Clinical evaluation	Patient status	
	Concomitant therapy	Pain medication
	AKSS*	
	Patient questionnaires	SF-36 EQ-5D
Radiographic assessment	Anterior/posterior Lateral Radiostereometric analysis	

Complications		
---------------	--	--

Termination

Date of evaluation		
Study completion	Reason for early termination	
Position of study device at last contact to patient		
Problems at last contact		

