3.2. Number of Subjects

RSA is able to measure wear with high accuracy. Previous RSA wear studies show that the expected wear rate is 0.13 ± 0.08 mm a year (Short et al., 2005; Kellett et al., 2004). A clinical relevant difference to detect differences in wear would be a standard deviation of 0.1 mm a year.

Group sample sizes of 27 patients in each group would achieve 95% power to detect a difference of -0.1 mm wear between the null hypothesis that both group means are 0 and the alternative hypothesis that the mean of group 2 is 0.1 with estimated group standard deviations of 0.1 and with a significance level (alpha) of 0.05 using a two-sided two-sample t-test.

However, in order to also achieve the third objective of this protocol whereby clinical parameters will be correlated with RSA results, more patients are needed to obtain stronger correlations with the important

clinical outcome parameters. Taking the latter in account and to compensate for possible lost to follow up, 50 patients will be recruited per study group.

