4.3.1 Specific Criteria for Withdrawal /Termination

In the event that a subject is discontinued from the study for any reason, the site will complete a Study Termination form. Subjects may be withdrawn for the following reasons:

- Patient failure – defined by the requirements at the two- year follow-up interval see section 6.1.3.
- Any Serious Adverse Event that effects the outcome of the study
- Any Serious Adverse Event related to the test device
- Revision/Removal of study device
- Patient withdrawal (patients own request)
- Lost to Follow-Up

- If, in the Investigator's opinion, continuation in the study would be detrimental to the subject's well being (a written explanation is required)
- Completion of study and final evaluation
- Death of the subject

If the patient fails to return for their follow-up appointments, every effort should be made to contact the subject to assess their health status. If after attempting to contact the patient through 3 documented phone calls and a certified (i.e., return-receipt) letter, the patient still does not respond, the patient will be considered as "lost to follow-up". A Study Termination Form will be completed after notifying Stryker of the patient's status.

In the event that the subject is discontinued by the investigative site prior to the final study evaluation, the subject is notified that they are no longer in the study and a Study Termination form will be completed.

Following discontinuation, the subject will be seen regularly as considered clinically appropriate. If the discontinuation was caused by an adverse event the subject will be seen regularly until the symptoms have disappeared or are under control, or until feasible treatment has been undertaken. Refusal to participate or early withdrawal from this investigation will not affect the quality or availability of the subject's medical care.

Subjects withdrawn from the study will keep their subject number. New subjects must always be assigned a new subject number. In the event that the subject withdraws from this investigation, the information that has already been collected will be included in the database and in the final analyses. The subject's medical records will also be available for monitoring, auditing and inspection purposes.

After withdrawal subjects will not be replaced to the study.

5. Subject Enrolment

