7.2. Definitions

Adverse Event (AE) – “Any untoward medical occurrence in a subject whether it is considered to be device related or not. An adverse event can therefore be any unfavourable and unintended sign, symptom, or disease developed or worsened during the period of observation in the study, whether or not related to the investigational product”

An Adverse Event could be:

- a new illness
- worsening of an illness
- an effect of the study device including the comparator (if any)
- a combination of two or more of these factors

Surgical procedures themselves are not Adverse Events; they are therapeutic measures for conditions that require surgery. The condition for which the surgery is required is an adverse event if it occurs or is detected during the study period. Planned surgery measures permitted by the study and the condition(s) leading to these measures are not adverse events. If the condition(s) was (were) known before the subject enrolled in the study, this (these) should be recorded in the medical history CRF.

Adverse Device Effect (ADE) – “Any untoward or unintended response to a medical device including any event resulting from insufficiencies or inadequacies in the instructions for use or the deployment of the device and any event that is a result of user error”

Serious Adverse Event (SAE) – An adverse event that:

- Led to a death, or
- Led to serious deterioration in the health of the subject that:
 - resulted in a life-threatening illness or injury.
 - resulted in a permanent impairment of a body structure or a body function.
 - required in-patient hospitalization or prolongation of existing hospitalization.
 - resulted in medical or surgical intervention to prevent permanent impairment to body structure or a body function, or
- Led to foetal distress, foetal death or a congenital abnormality or birth defect.

The term “life threatening” in the definition refers to an event in which the subject was at risk of death at the time of the event. It does not refer to an event that hypothetically might have caused death if it were more severe.

Serious Adverse Device Effect (SADE) – “adverse device effect that has resulted in any of the consequences characteristic of a serious adverse event or that might have led to any of these consequences if suitable action had not been taken or intervention had not been made or if circumstances had been less opportune”

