9.2. Missing Data

No imputation of missing data will be made. If any questionnaire (e.g., AKSS) has a missing item, the total score for that scale will be considered missing.

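### No RSA or scores are required at early exit or before a revision, so outcome-related losses can leave the 5-year wear value missing

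*Combined protocol and SAP*

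**What the plan says.** **Measurement times.** Table 1 and section 6.3 place RSA before discharge, at 6 weeks, 3 and 6 months, 1 year (double), 2 years and 5 years. The Knee Society Score and questionnaires follow the same calendar from 6 weeks on. Table 1 has no column for early termination or for the time before a revision.

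**Exit data.** The Termination list in section 6 has four entries: date of evaluation, study completion with the reason for early termination, "Position of study device at last contact to patient", and problems at last contact.

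**Who may leave.** Section 4.3.1 says that subjects may be withdrawn for, among other reasons, "Revision/Removal of study device", a device-related serious adverse event, or patient failure as defined in 6.1.3. A Knee Score below 80 at two years is enough to count as failure. Data already collected stay in the final analyses, and withdrawn subjects are not replaced.

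**Analysis.** Section 2 states the wear hypothesis at 5 years and the migration hypothesis at two years. Section 9.1 names t-tests or rank tests, and section 9.2 states "No imputation of missing data will be made". No section says how a revised implant enters the wear comparison.

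**Recording of revisions.** A row of Table 1 begins "Adverse Events (including revision", to be reported at any time. Section 7.2 says "Surgical procedures themselves are not Adverse Events; they are therapeutic measures for conditions that require surgery", then adds that the condition requiring the surgery is an adverse event.

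**The concern.** Section 6.3 measures wear as the change in position of the femoral component relative to the tibial component since baseline. Once the insert or either component is exchanged, that chain is broken and the wear of the randomised insert cannot be recovered. A film taken before the exchange is the last chance to measure it, and the plan does not ask for one.

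The loss is tied to outcome. Revision, device-related events and two-year failure are all permitted reasons for withdrawal, so the patients without a 5-year reading may differ systematically from those with one. If the missing patients are mainly high-wear N2Vac patients, the observed difference shrinks. If they are mainly high-wear X3 patients, it grows. A patient who leaves before two years can also lack the 2-year migration value.

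**Working it through.** **1. The plan's own figure.** Inputs from section 3.2: "Group sample sizes of 27 patients in each group would achieve 95% power to detect a difference of -0.1 mm wear", with "estimated group standard deviations of 0.1 and with a significance level (alpha) of 0.05 using a two-sided two-sample t-test". The normal approximation gives n = 2 × (1.960 + 1.645)² × (0.1/0.1)² = 25.99, so 26 per group. The exact noncentral t calculation gives 26.99, so 27, with power 0.9501. The stated 27 reproduces.

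**2. Is power the issue?** With 50 recruited per arm, t-test power under the same inputs is:
- no loss (50 per arm): 0.9986
- 10% loss (45): 0.9968
- 20% loss (40): 0.9930
- 46% loss (27): 0.9501

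Loss of numbers alone does little harm. What matters is which patients are lost.

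**3. Bias from a few selective losses.** Section 3.2 says "the expected wear rate is 0.13 ± 0.08 mm a year". Assume that 2 of 50 N2Vac patients, with wear z SD above the mean, have no 5-year value. The shift in the N2Vac mean is (k/n) × z × SD:
- z = 2: (2/50) × 2 × 0.08 = 0.0064 mm a year
- z = 3: (2/50) × 3 × 0.08 = 0.0096 mm a year

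Over 5 years this is 5 × 0.0064 = 0.032 mm to 5 × 0.0096 = 0.048 mm. Reading the 0.1 mm target as a yearly rate, the shift is 6.4% to 9.6% of it. The same two losses in X3 instead, with the same SD, would move a true difference of 0.1 up to 0.1064 to 0.1096. Equal selective loss in both arms would largely cancel.

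**4. Larger losses.** Assume normally distributed wear, a true difference of 0.1, and the highest-wearing fraction q missing from N2Vac only. The N2Vac mean falls by SD × φ(c)/(1 − q), where φ is the standard normal density and c its upper-q quantile. The observed difference becomes:

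| q | SD 0.10 | SD 0.08 |
|---|---|---|
| 2% | 0.0951 | 0.0960 |
| 5% | 0.0891 | 0.0913 |
| 10% | 0.0805 | 0.0844 |
| 20% | 0.0650 | 0.0720 |

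The effect is small at 2 to 5% and material at 10 to 20%. This is a worst case, because it removes exactly the highest wearers from one arm only.

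**5. Age of the last reading.** A patient revised at month 50 was last due for RSA at month 24, so the last scheduled film is 50 − 24 = 26 months old. The 2-year migration value exists for this patient; only the later wear information is lost.

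**The case against.** The best defence is that much of the record survives. Section 4.3.1 keeps all data collected before withdrawal and makes withdrawal permissive. The migration objective is set at two years, so a later revision costs it nothing. The assumed wear bias is under a tenth of the target difference, no rate in the protocol supports any particular count, and power is ample. These points stand, and they limit the size of the problem.

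They also rule out four stronger readings that a reader might infer:
- *Failed implants vanish from the survival results.* They do not. Revision is a durability endpoint in 6.1.2, a failure criterion in 6.1.3 and a termination reason in 4.3.1.
- *The third objective needs RSA close to failure.* Section 2 bases that prediction on two-year migration patterns.
- *No form records revisions.* The condition behind the surgery is an adverse event under 7.2, and serious if it leads to hospitalisation. Table 1 collects revision at any time. The termination reasons include study completion, so completers appear to get the form too. The case report form itself is not in the text reviewed. The mismatch between Table 1 and 7.2 is one of wording.
- *A large share of revisions goes uncounted.* Assuming 3% revision in attenders, 10 to 20% non-attendance and a two- to threefold rate in non-attenders gives 0.6/3.3 = 18% to 1.8/4.2 = 43%. None of these inputs is in the protocol. The result also assumes that no revision in a non-attender is ever found, whereas 4.3.1 requires three documented calls and a certified letter before loss is declared.

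What the defence does not answer is that an exchanged insert's wear is lost for good, for reasons linked to outcome, when one examination could have captured it.

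**Conclusion.** The gap is real and narrow. A patient who is revised, or withdrawn for an outcome-related reason, can lack the 5-year wear value, and one who exits before two years can lack the 2-year migration value. Nothing is imputed.

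The bias is probably modest, about 0.006 to 0.010 mm a year under the assumption of two high-wear N2Vac losses. It becomes material only if 10% or more of one arm is lost selectively. Its direction cannot be known in advance. The sample size of 27 needed and 50 recruited per arm is unaffected. The case for change rests on low cost and on data that cannot be recovered later.

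**What to change.** 1. **Closing measurement.** Add to the Termination list and to Table 1: *RSA pair, Knee Society Score and questionnaires at early termination and before any planned revision, where feasible and if the patient agrees.* State in section 9 that this film is used as wear per year at its actual time since surgery, or in a longitudinal model, in an analysis alongside the 5-year comparison. Without that sentence, the film has no place in a 5-year t-test.
2. **Retention.** Keep patients classed as two-year failures, whose study components are still in place, in study follow-up for the 5-year RSA.
3. **Revision record.** Record each revision or removal as its own case report form item (date, component, reason) and align Table 1 with section 7.2. At the 5-year close, check revision status in hospital records for all randomised patients who have not withdrawn authorization (section 11.5).

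**Cost.** One additional RSA pair in a few patients, at the 3 µSv per RSA radiograph given in section 8.2, one form item, and a records check at a single hospital. A patient who leaves before year 5 forgoes the 5-year film and so does not exceed the number of examinations in Table 1; a revised patient who stays in the study may have one more. Urgent revisions may miss the film, and revisions done at other hospitals may be missed by the records check.

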6.1. Study parameters/endpoints

6.1.1 Clinical outcome

- Relief of Pain, measured by an increase in the pain score component of the Knee Society Score
- Restoration of Function, measured by an increase in the functional score of the Knee Society Score.
- Patient satisfaction as determined by answers to patient outcomes questionnaires (EQ 5-D, SF-36 and Lower Extremity Activity Scale).

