Roentgen Stereophotogrammetric Analysis (RSA) is a very accurate measurement technique used to obtain micromotion of the implants relative to inserted tantalum markers in the surrounding bone. The accuracy of RSA mentioned in the literature ranges from 0.01 to 0.7 mm for displacement. It has been applied in many studies, mostly in Sweden (Kärrholm, 1989). In 2000, the Orthopaedic Department of the Leiden University Medical Center developed a Model-based RSA system (Model-based RSA, Medis specials BV, Leiden, The Netherlands). The accuracy of this software in clinical studies is about 0.25 mm for translations and 0.2° for rotations in the 95% confidence interval (Hurschler et al., 2006; Kaptein et al., 2003; Vrooman et al, 1998). Kärrholm et al. (1994) and Ryd et al. (1995) showed that with RSA a long-term prediction can be made of prosthetic loosening based on a two years follow-up.

The goal of this study is to compare conventional UHMWPE with X₃ highly cross-linked polyethylene in a CS fixed bearing total knee prosthesis (Triathlon Knee System: Stryker, Warsaw, USA) by means of RSA and clinical evaluation.

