9.1. Statistical Methods

Continuous outcome variables and their differences will be analyzed with parametrical statistical techniques, such as t-tests, unless the normality assumption does not seem reasonable for the data, in which case non-parametric techniques will be considered e.g. Wilcoxon/Mann-Whitney tests.

Categorical outcome variables will be analyzed with chi-square tests and/or Fisher's exact tests (depending on the expected values in the categories). For the relevant parameters (subsidence, survival, pain and function) also the 95 percent confidence intervals will be calculated.

The effect of parameters such as age, sex and operators will be evaluated using multiple variate analysis. All data will be analyzed by blinded researchers.

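### Section 9.1 names only t-tests or rank tests for clinical scores taken at six follow-up visits, leaving up to 30 unadjusted between-arm comparisons open; one repeated-measures model per score would cut these to five

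*Combined protocol and SAP*

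**What the plan says.** - **Goal.** Section 1.1 sets out to compare the two polyethylenes "by means of RSA and clinical evaluation", so clinical evaluation is part of the comparison between inserts.
- **Scores.** Section 6.1.1, under the study endpoints, lists the pain component and the functional score of the Knee Society Score, then "Patient satisfaction as determined by answers to patient outcomes questionnaires (EQ 5-D, SF-36 and Lower Extremity Activity Scale". The five are not ranked.
- **Visits.** Section 6 has patients evaluated pre-operatively, "prior to discharge and at follow-up intervals of 6 weeks, 3 months, 6 months, 1, 2 and 5 years". Table 1 marks the Knee Society Score, SF-36, EQ-5D and LEAS pre-operatively and at all six visits from 6 weeks to 5 years. The follow-up list later in section 6 names the SF-36 and EQ-5D but not the LEAS.
- **Analysis.** Section 9.1: "Continuous outcome variables and their differences will be analyzed with parametrical statistical techniques, such as t-tests", with rank tests as the fallback. It adds 95% confidence intervals for a short list of parameters that includes pain and function. It names no visit, no repeated-measures model, no test level for clinical scores and no multiplicity rule.
- **Alpha.** A significance level appears once, in the wear sample size of section 3.2: "with a significance level (alpha) of 0.05 using a two-sided two-sample t-test".
- **Ranking of objectives.** The Study Summary names one primary endpoint, wear. Section 2 ranks wear first, migration second and prediction of survival third. Clinical scores enter those objectives only as variables to be correlated with the RSA results.

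**The concern.** The scores are repeated measurements on the same patients, but the only named methods are tests suited to one measurement per patient. An analyst following section 9.1 could test any score at any of six visits, as a raw value or as a change, and nothing says which result counts. Blinding the analysts, as sections 5.3 and 9.1 provide, does not limit how many comparisons are made.

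What is at stake is the clinical claim. The documents give no expected clinical difference between inserts and no power for one. Section 16 anticipates publication. One nominally significant score at one visit could be reported as a clinical difference, for or against X3, with no rule in the plan for telling it from chance.

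**Working it through.** **1. The plan's own figure.** Section 3.2 states: "Group sample sizes of 27 patients in each group would achieve 95% power to detect a difference of -0.1 mm wear", with "estimated group standard deviations of 0.1" and two-sided alpha 0.05.

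Normal approximation: n = 2 x (1.960 + 1.645)² x (0.1/0.1)² = 2 x 13.0 = 26 per group. With the noncentral t distribution, power is 0.942 at 26 and 0.950 at 27. The stated 27 reproduces. It concerns wear only; the documents give no error rate for the clinical scores.

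**2. Number of comparisons left open.**
- Table 1: 5 scores x 6 visits = 30.
- Without the LEAS: 4 x 6 = 24.
- The plan does not say which SF-36 or EQ-5D score is used. One further score would make 6 x 6 = 36.

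**3. Expected false positives if the inserts do not differ clinically and each comparison is tested at 0.05.** 30 x 0.05 = 1.5, whatever the correlation. For 24 comparisons: 24 x 0.05 = 1.2.

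**4. Chance of at least one, if independent.** 1 - 0.95^k:
- k = 24: 0.71
- k = 30: 0.79
- k = 36: 0.84

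**5. Chance of at least one, if correlated.** Scores within a patient are correlated across instruments and visits, which lowers the figure. The documents give no correlations, so these are assumptions. The results come from simulating 30 two-sided z-tests under the null (200,000 draws per setting). The correlation between two tests is the between-score value multiplied by the between-visit value.

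| Between scores | Between visits | At least one of 30 |
|---|---|---|
| 0 | 0 | 0.79 |
| 0.3 | 0.5 | 0.65 |
| 0.5 | 0.5 | 0.60 |
| 0.5 | 0.7, decaying serially | 0.58 |
| 0.5 | 0.7 | 0.50 |
| 0.7 | 0.7 | 0.42 |
| 0.8 | 0.9 | 0.25 |

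A single common correlation of 0, 0.3, 0.5, 0.7 or 0.8 between all 30 tests gives 0.79, 0.66, 0.51, 0.34 and 0.26. With 24 comparisons the range is 0.24 to 0.71.

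**6. After the change.** One overall arm contrast per score leaves five comparisons, with 5 x 0.05 = 0.25 false positives expected. The chance of at least one is 1 - 0.95^5 = 0.23 if independent, 0.18 at a between-score correlation of 0.5, and 0.13 at 0.8.

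**The case against.** The strongest reply is that the plan does not prescribe 30 tests. Section 9.1 gives examples of methods, does not call for a test at every visit, and sets no level for clinical scores; the 0.05 belongs to the wear calculation. This stands. A reader might infer that every score will be tested at every visit at full alpha, but the documents only leave that open.

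Second, the trial has a hierarchy. Wear is the single primary endpoint, migration comes next, and section 2 states an expected difference between inserts for those two only. Section 9.1 singles out pain and function for confidence intervals, and section 6.1.3 fixes a two-year success criterion that uses the Knee Score. This also stands, so it would be wrong to say that the plan has no ordering at all. But neither provision names a lead clinical score or limits how the five scores are compared between arms, which section 1.1 makes part of the goal.

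Third, formal gatekeeping of supportive scores in a 100-patient post-marketing RSA study is a design preference. Agreed: testing one score only after wear is optional and is not needed to meet this point.

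**Conclusion.** The point holds as a gap in the method for the clinical scores. Section 9.1 leaves up to 30 unadjusted comparisons open (24 without the LEAS). If all were made at 0.05 with no true clinical difference, 1.5 would be significant on average. The chance of at least one would be about 25% to 79%; even the lowest 30-test setting examined is five times the nominal 5%. The range rests on assumed correlations and on the count of scores.

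Two stronger readings are not supported. A reader might say that a chance clinical difference is about as likely as not; that is the result near correlations of 0.5 between scores and 0.7 between visits, and it is not a finding from the documents. A reader might also say that any significant clinical score is more likely noise than effect. That would need a prior and a power for a clinical effect, and the documents give neither.

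The wear comparison and its sample size are untouched. The consequence is confined to secondary clinical claims.

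**What to change.** In section 9.1:

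1. Compare the arms on each clinical score with one repeated-measures model over all six follow-up visits, with the pre-operative score as covariate, in place of separate tests per visit. Name one overall arm contrast per score. If the rank-based fallback is kept, apply it once per score to a patient-level summary over visits.
2. State that the clinical scores are supportive to wear and migration.
3. Report them as estimates with 95% confidence intervals, extending what section 9.1 already plans for pain and function. Visit-specific differences can be shown the same way, without claims of significance.
4. State which SF-36 and EQ-5D scores are used, and reconcile the LEAS between Table 1 and the follow-up list in section 6.

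Gating one named score behind wear may be added but is optional.

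**Cost.** A few sentences and no new data: Table 1 already collects the pre-operative scores. A likelihood-based model uses the visits each patient has, which fits the rule in section 9.2 against imputation. There are two downsides. An isolated p < 0.05 on one score at one visit can no longer be claimed as a clinical difference. An overall contrast also averages early and late visits, so a difference confined to 5 years would appear only in the visit-specific estimates.
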